5.3.2. General Data Handling Rules

Missing data will be handled depending on the assumed mechanism behind the missingness, whether the endpoint is a key endpoint, and the estimand being used. Handling rules are summarized in Table 5 below:

Table 5: Data Handling Rules for Missing Data

Estimand	imand Assumption Continuous endpoints		Binary response endpoints
Estimand	Assumption MAR (Missing at Random) due to Natural Disaster or Major Disruption MAR NOT due to	Continuous endpoints Major secondary endpoint: imputed using Full Conditional Specifications (FCS) MI Clinical Other endpoints: not imputed but accounted for in MMRM model Major secondary endpoints:	Binary response endpoints Primary and Major secondary endpoints: imputed using Full Conditional Specifications (FCS) MI on continuous component scale then dichotomized Clinical Other endpoints: not imputed but accounted for in GLMM Primary and Major secondary
Adjusted Composite	above reasons	imputed using Full Conditional Specifications (FCS) MI Clinical Other endpoints: not imputed but accounted for in MMRM model	endpoints: conservatively imputed as non-response for consistency with historical studies Clinical Other endpoints: conservatively imputed as non-response for consistency with historical studies
	Missing Not at Random (MNAR)	N/A	Primary endpoints: For tipping point analyses specifically: Sensitivity analysis with exhaustive assessment of all possible combinations of response status for missing data
	MAR	Major secondary endpoints: imputed using FCS MI	Primary and Major secondary endpoints: imputed using FCS MI on continuous component scale then dichotomized
Treatment Policy	MNAR	Major secondary endpoints: For tipping point analyses specifically: Supplementary analysis systematically assessing scenarios which deviate from MAR or MCAR assumption	Primary and Major secondary endpoints: For tipping point analyses specifically: Supplementary analysis systematically assessing scenarios which deviate from MAR or MCAR assumption
	MCAR	Other Efficacy endpoints: not imputed	Other Efficacy endpoints: not imputed

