- 5. (Supplementary Analysis 1) To support regulatory decision making, the Treatment Policy Estimand (Section 5.3.4.2) will also be evaluated as a supplementary analysis. In this analysis, the observed ACR 20 response for all participants will be used regardless of whether or not ICE criteria are met prior to Week 24, and the missing ACR 20 response will be imputed by FCS MI (Section 5.3.2.1) on the component level under the assumption that data are MAR. Treatment comparisons for each imputation data set will be based on a CMH test stratified by baseline use of non-biologic DMARDs (yes, no), as per Section 5.3.1. This analysis will be conducted based on the FAS-UKR analysis set.
- 6. (Supplementary Analysis 2) An additional tipping point analysis for the Treatment Policy Estimand will be performed. The observed ACR 20 response for participants will be used regardless of whether or not ICE criteria are met prior to Week 24, and the missing ACR 20 response will be imputed by FCS MI (Section 5.3.2.1) on the component level under the assumption that data are MAR. In this analysis, a pair of deltas will be added to the predicted response rates from MI method depending on guselkumab or placebo group to new MI datasets (Section 5.3.2) to evaluate deviation from the assumption of MAR for missing data. The same analysis method as in the primary analysis will be applied for the pairs of deltas. The analysis will be done for pairs of delta values include the scenarios where participants on

guselkumab have worse outcomes than participants on placebo. This analysis will be conducted based on the FAS-UKR analysis set.

Subgroup Analyses

Subgroup analyses will be performed using the Adjusted Composite Estimand using a logistic regression model on the multiply imputed data to evaluate treatment consistency in proportion of participants who achieve an ACR 20 response at Week 24 over baseline demographics, baseline disease characteristics, and prior and baseline medication use. A forest plot will be produced for all subgroups listed in Section 5.5.5. The odds ratios and the corresponding 95% CIs will also be provided for each of the subgroups (Section 5.3.1). In addition, the p-values for interaction of the intervention groups and the subgroups will also be provided when a subgroup has at least 2 categories.

If the number of participants in a subgroup is too small (eg, <10), subgroups may be pooled for analyses.

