5.3.5.4.1. Definition

5.3.5.4.2. Analysis Methods

The change from baseline in HAQ-DI score at Week 24 will be analyzed at Week 24 DBL based on the Adjusted Composite Estimand (Section 5.3.4.2). In this analysis, data from all subjects in

FAS (Section 4.2) will be analyzed according to randomized treatment group regardless of the treatment received.

Analysis of the change from baseline in HAQ-DI score at Week 24 will be performed using an ANCOVA model based on MI data. The MI method will be applied to impute for missing data, under the assumption of MAR, the missing change score of HAQ-DI from baseline at Week 24 defined in the Adjusted Composite Estimand (ie, change from baseline with no change assumed at and after meeting ICE (1-3) criteria). The treatment difference between each guselkumab group versus the placebo group will be tested for each imputation dataset and then the analysis results across all imputation datasets will be combined.

To support regulatory decision making, a supplementary analysis will be provided in FAS-URK based on the Treatment Policy Estimand. Analysis of the change from baseline in HAQ-DI score at Week 24 will be performed using an ANCOVA model based on MI data similar to the main analysis.

5.3.5.5. Change from Baseline in SF-36 PCS Score at Week 24

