1	 Proportions of participants with ACR 20 response at Week16 Proportions of participants with ACR 50 response at Week16/Week24 Proportions of participants with ACR 70 response at Week24 	FAS	Missing data due to Natural Disaster or Major Disruption assumed MAR, imputed via FCS MI Missing data not due to Natural Disaster or Major Disruption assumed MAR but conservatively imputed as non-response	Summarized descriptively Response rates, treatment difference in response rates and 95% CI p-value from the CMH statistic with Wilson- Hilferty transformation across multiply imputed data sets
2	Change from baseline in HAQ-DI score / SF-36 PCS score / FACIT-F score at Week24	FAS	Missing data for any reason assumed MAR, imputed via FCS MI	 Summarized descriptively ANCOVA for each MI dataset and then analysis results across all MI datasets combined LS mean (95% CI) for each intervention group, LS mean difference (95% CI) between groups, p-values for differences between groups

 $CONFIDENTIAL-FOIA\ Exemptions\ Apply\ in\ U.S.$

[figure not shown]
3	Proportion of participants with IGA response / PASI90 response	FAS with ≥3% BSA and IGA≥2 at baseline	Missing data due to Natural Disaster or Major Disruption assumed MAR, imputed via FCS MI Missing data not due to Natural Disaster or Major Disruption assumed MAR but conservatively imputed as non-response	Summarized descriptively Response rates, treatment difference in response rates and 95% CI p-value from the CMH statistic with Wilson-Hilferty transformation across multiply imputed data sets
4	Proportion of participants with MDA response	FAS	Missing data due to Natural Disaster or Major Disruption assumed MAR, imputed via FCS MI Missing data not due to Natural Disaster or Major Disruption assumed MAR but conservatively imputed as non-response	Summarized descriptively Response rates, treatment difference in response rates and 95% CI p-value from the CMH statistic with Wilson-Hilferty transformation across multiply imputed data sets

ENDPOINTS AT WEEK-24 DBL USING TIPPING POINT ANALYSIS WITH TREATMENT POLICY ESTIMAND AND The FAS-UKR ANALYSIS SET INSTEAD OF FAS

The endpoints analyzed using the Adjusted Composite Estimand for corresponding visits/DBL are repeated here, except:

- All observed data will be used, regardless of whether or not the subjects meet any ICEs.
- Missing data assumed MAR, imputed via FCS MI regression.
- Two-dimensional tipping point analysis will be used.

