Handling Rules for Missing Binary Data for Adjusted Composite Estimand

- 1. Missing data due to Natural Disaster (caused site closure, site access restrictions, or lockdowns) or Major Disruption will be assumed to be MAR. The data is not explicitly imputed but is accounted for in the analysis model.
- 2. Missing data for any other reason will be assumed to be MAR but conservatively imputed as NR.

Analysis Testing for Adjusted Composite Estimand

Statistical comparison between a guselkumab group (100 mg q4w or 100 mg q8w) and the placebo group will be performed by visit through Week 24 using the MMRM model for continuous endpoints and the GLMM for binary response endpoints (see Appendix 13 in Section 6.13). No treatment comparison will be performed after Week 24. For continuous endpoints, only descriptive summaries and LSmeans by study intervention and visit will be presented after Week 24 through Week 100; for binary endpoints, only descriptive summaries and model-based response rates by study intervention and visit will be presented after Week 24 through Week 100.

ICE Strategies for Treatment Policy Estimand

For the Treatment Policy Estimand, the occurrence of ICEs is considered irrelevant. This estimand looks at the effect of assignment to intervention group irrespective of changes to background PsA medications, study intervention adherence, or study retention.

Handling Rules for Missing Data for Treatment Policy Estimand

1. **Missing data for any reason** will not be imputed, assumed to be MCAR.

Analysis Testing for Treatment Policy Estimand

A corresponding supportive analysis will be conducted using the Treatment Policy Estimand. For these analyses, the FAS-UKR analysis set or further subset (if specified) will be used. For visits through Week 24, an ANCOVA model will be used for continuous endpoints, and the CMH test for treatment difference and 95% CI calculated based on Wald statistics will be used for the binary response endpoints. No treatment comparison will be performed after Week 24. For continuous endpoints, only descriptive summaries and LSmeans by study intervention and visit will be presented after Week 24 through Week 100; for binary endpoints, only descriptive summaries of response rates by study intervention and visit will be presented after Week 24 through Week 100.

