Table 8 summarizes the analyses for supportive efficacy endpoints related to reduction of signs and symptoms and physical function, the methods for analyses, and the data handling rules used.

Table 8: Summary of Estimands, Analysis Sets, Data Handling Rules, and Analysis Methods for Endpoints of Signs & Symptoms and Physical Function

	Endpoint	Analysis Set	Missing Data Rules	Analysis Methods		
	ENDPOINTS BY VISIT THROUGH WEEK 24 AT WEEK-24 DBL, ADJUSTED COMPOSITE ESTIMAND					
1	Proportions of participants with ACR 20, ACR 50, and ACR 70 response	FAS	NRI for MAR not due to Natural Disaster or Major Disruption	Summarized descriptively Response rates, and treatment difference in response rates and 95% CI and p-value, based on GLMM		
2	Change from baseline in ACR components	FAS	-	 Summarized descriptively LS mean (95% CI) for each intervention group 		
3	Change from baseline in HAQ-DI score	FAS	-	Summarized descriptively LS mean (95% CI) for each intervention group, LS mean difference (95% CI) and p-values for differences between groups based on MMRM		
4	Proportion of participants with HAQ-DI response	FAS whose baseline HAQ- DI score ≥0.35	NRI for MAR not due to Natural Disaster or Major Disruption	 Summarized descriptively Response rates, and treatment difference in response rates and 95% CI and p-value, based on GLMM 		

Table 8: Summary of Estimands, Analysis Sets, Data Handling Rules, and Analysis Methods for Endpoints of Signs & Symptoms and Physical Function

	Endpoint	Analysis Set	Missing Data Rules	Analysis Methods
5	Proportion of participants who achieve resolution of enthesitis	FAS with enthesitis at baseline	NRI for MAR not due to Natural Disaster or Major Disruption	Summarized descriptively Response rates, and treatment difference in response rates and 95% CI and p-value, based on GLMM
6	Proportion of participants with resolution of dactylitis	FAS with dactylitis at baseline	NRI for MAR not due to Natural Disaster or Major Disruption	Summarized descriptively Response rates, and treatment difference in response rates and 95% CI and p-value, based on GLMM
7	Change from baseline in enthesitis score (based on Leeds Enthesitis Index [LEI])	FAS with enthesitis at baseline	-	Summarized descriptively LS mean (95% CI) for each intervention group, LS mean difference (95% CI) and p-values for differences between groups based on MMRM

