15	Proportion of participants who maintained an ACR 20 response at Week 52	FAS who achieved an ACR 20 response at Week 24	NRI for MAR not due to Natural Disaster or Major Disruption.	Summarized descriptively Response rates by intervention group based on GLMM
16	Proportion of participants who maintained an ACR 50 response at Week 52	FAS who achieved an ACR 50 response at Week 24	NRI for MAR not due to Natural Disaster or Major Disruption	 Summarized descriptively Response rates by intervention group based on GLMM
17	Proportion of participants who maintained an ACR 70 response at Week 52	FAS who achieved an ACR 70 response at Week 24	NRI for MAR not due to Natural Disaster or Major Disruption	Summarized descriptively Response rates by intervention group based on GLMM
18	Proportion of participants who maintained HAQ-DI response at Week 52	FAS who achieved HAQ-DI response at Week 24	NRI for MAR not due to Natural Disaster or Major Disruption	Summarized descriptively Response rates by intervention group based on GLMM

ENDPOINTS BY VISIT AFTER WEEK 52 THROUGH WEEK 100 AT WEEK-112 DBL, ADJUSTED COMPOSITE ESTIMAND

Table 8: Summary of Estimands, Analysis Sets, Data Handling Rules, and Analysis Methods for Endpoints of Signs & Symptoms and Physical Function

	Endpoint	Analysis Set	Missing Data Rules	Analysis Methods
1, 4, 5, 6, 10, 11, 15, 16, 17, 18	Same as through Week 52	Same as through Week 52	Same as through Week 52	Summarized descriptively Response rates by intervention group based on GLMM
2, 3, 7, 8, 9, 12, 13, 14	Same as through Week 52	Same as through Week 52	Same as through Week 52	Summarized descriptively LSMeans and 95% CI by intervention group based on MMRM model

ENDPOINTS BY VISIT THROUGH WEEK 24 AT WEEK-24 DBL,
AFTER WEEK 24 THROUGH WEEK 52 AT WEEK-52 DBL,
AFTER WEEK 52 THROUGH WEEK 112 AT WEEK-112 DBL, USING TREATMENT POLICY
ESTIMAND AND THE FAS-UKR ANALYSIS SET INSTEAD OF FAS

The endpoints analyzed using the Adjusted Composite Estimand for corresponding visits/DBL are repeated here, except:

- No imputation will be applied, and all analyses will be based on observed data.
- Continuous endpoints will use ANCOVA instead of MMRM; binary response endpoints will use CMH test
 with CI based on Wald statistics instead of GLMM for visits up to and including Week 24.

[figure not shown]

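### Supportive Treatment Policy analyses of the other efficacy endpoints use observed cases under MCAR and, for endpoints that are also primary or major secondary, add a second, unranked estimate beside the MAR one

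*SAP*

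**What the plan says.** **Other efficacy endpoints.** Under the Treatment Policy Estimand, SAP 5.3.6.2.9 states that missing data "will not be imputed, assumed to be MCAR". The analysis set is FAS-UKR, and groups are compared by visit through Week 24. Table 5 gives the same rule in its MCAR row ("Other Efficacy endpoints: not imputed"). The Treatment Policy block of Table 8, repeated in Tables 9 and 10, reads "No imputation will be applied, and all analyses will be based on observed data" and "Continuous endpoints will use ANCOVA instead of MMRM; binary response endpoints will use CMH test" in place of the GLMM.

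**Primary and major secondary endpoints.** Under the same estimand, the assumption is MAR with imputation:
- ACR 20 at Week 24 (5.3.4.4, Supplementary Analysis 1) is imputed "on the component level under the assumption that data are MAR", in FAS-UKR.
- HAQ-DI change at Week 24 (5.3.5.4.2): "a supplementary analysis will be provided in FAS-URK based on the Treatment Policy Estimand" (a misprint for FAS-UKR), by ANCOVA on multiply imputed data.
- The Treatment Policy block of Table 7, in 5.3.5.10, says "Missing data assumed MAR, imputed via FCS MI regression".

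**Overlap.** Table 8, by visit through Week 24, lists "Proportions of participants with ACR 20, ACR 50, and ACR 70 response", HAQ-DI change and MDA. Table 9 lists PASI 90, and Table 10 lists SF-36 PCS and FACIT-F change. All of these are also primary or major secondary endpoints at Week 24, and ACR 20 and ACR 50 are major secondary at Week 16 as well.

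**The concern.** Two things sit awkwardly together.

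First, the MCAR assumption is not argued for, and other parts of the SAP point away from it. A footnote to the Appendix 12 table keeps all seven ACR components, baseline through Week 24, among the ancillary variables because they may bear on why data are missing. The Treatment Policy Estimand is described in 5.3.6.2.9 as the effect of assignment regardless of retention. An observed-case analysis at a visit nevertheless drops everyone absent at that visit and ignores what was recorded on them earlier. The main analysis of the same continuous endpoints uses MMRM under MAR. Tipping-point analyses are planned only for the primary and major secondary endpoints, so the MCAR results have no sensitivity check.

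Second, for an overlapping endpoint such as ACR 20 at Week 24, the Week 24 report would hold two Treatment Policy results for the same endpoint, visit and analysis set, based on different missing-data assumptions. With any missing data they will generally differ, and the SAP does not say which one is the Treatment Policy result.

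**Working it through.** **1. What can be reproduced.** The documents give no missing-data rate and no figure for this point. The planning inputs used below do reproduce. HAQ-DI with 150 per arm, difference 0.25 and SD 0.56 gives 97.2% power (SAP Table 4: 97%). ACR 20 at 22% versus 52% gives 99.98% (Table 3: above 99%).

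**2. Continuous illustration: HAQ-DI change.** Means are -0.07 (placebo) and -0.32 (guselkumab q8w), SD 0.56, true difference -0.25 (SAP Table 4, PSA3001). Assumed, not documented: the missing rates, a correlation of 0.5 or 0.7 between an interim change and the Week 24 change, and missingness logistic in the interim change with slope 0, 0.5 or 1.0 log-odds per SD. The simulation used 400,000 per arm and no baseline covariate. Observed-case differences, as the pair for correlation 0.5 and 0.7:

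| Missing, placebo / guselkumab | slope 0 | slope 0.5 | slope 1.0 |
|---|---|---|---|
| 5% / 5% | -0.248, -0.248 | -0.251, -0.251 | -0.249, -0.249 |
| 10% / 10% | -0.250, -0.250 | -0.250, -0.251 | -0.251, -0.250 |
| 10% / 5% | -0.248, -0.250 | -0.245, -0.241 | -0.238, -0.232 |
| 15% / 5% | -0.250, -0.249 | -0.237, -0.232 | -0.226, -0.216 |
| 20% / 10% | -0.250, -0.249 | -0.236, -0.232 | -0.227, -0.218 |

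Regression imputation by arm under MAR gave -0.247 to -0.252 throughout. That is expected, because the data were generated to be MAR. The largest observed-case shortfall is 0.250 - 0.216 = 0.034, and 0.034 / 0.25 = 14%. There is none when missingness is MCAR or has the same rate and dependence in both arms.

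**3. Binary illustration: ACR 20.** Observed rate = (p - m·f·p) / (1 - m), where p is the arm's true rate, m the share missing, and f·p the response rate among the missing. With p = 22% and 52% (true difference 30.0 points), and m and f assumed:

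| Missing, placebo / guselkumab | f = 1 | f = 0.5 | f = 0 |
|---|---|---|---|
| 5% / 5% | 30.0 | 30.8 | 31.6 |
| 10% / 10% | 30.0 | 31.7 | 33.3 |
| 10% / 5% | 30.0 | 30.1 | 30.3 |
| 15% / 5% | 30.0 | 29.4 | 28.9 |
| 5% / 15% | 30.0 | 34.0 | 38.0 |

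For example, 5% / 15% with f = 0: 0.22 / 0.95 = 23.2%, 0.52 / 0.85 = 61.2%, difference 38.0. The range around 30 is -1.1 to +8.0 points, so the error can go either way. A MAR model would recover the true difference only as far as earlier visits explain who is missing.

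**4. Same check on the PSA3003 rates (19.8% and 44.4%).** With 15% / 5% missing, all non-responders: 0.198 / 0.85 = 23.3%, 0.444 / 0.95 = 46.7%, difference 23.4 points against 24.6. That is 1.2 points towards the null.

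**5. Analysis sets for the overlap.** ACR 20 at Week 24 and HAQ-DI change are in FAS-UKR on both sides, and SF-36 PCS follows the HAQ-DI section. SAP 5.3.5.2.2 puts the Treatment Policy analysis of IGA response in FAS, and the sections on PASI 90 and on ACR 50, ACR 70 and Week 16 ACR 20 refer back to it. Table 7 and Appendix 12 give FAS-UKR for all of these. For MDA and FACIT-F, only Table 7 and Appendix 12 can be read.

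**The case against.** The strongest reply is that this is prespecified tiering. Table 5 separates the tiers openly, 5.3.6.2.9 and Tables 8 to 10 agree with it, and 5.3.1 and Appendix 13 also provide for observed-case analysis under MCAR. A reader might infer that the SAP contradicts itself, and it does not. What remains is that both results answer one question and neither is ranked.

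A reader might also infer that every other endpoint gets two Treatment Policy estimates. Only the overlap does. VLDA, DAPSA, PASDAS, BASDAI, enthesitis, dactylitis, PROMIS-29 and PsAID-12 have no MI version.

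Nor do the documents support calling the observed-case results biased as a fact. The ANCOVA adjusts for baseline score and non-biologic DMARD use, so it remains valid if missingness depends only on treatment and those two. Protocol 7.2 encourages participants who stop study drug before Week 24 to keep attending through Week 24, and the estimand uses those data, so only study exits and missed visits are lost. With more placebo missing, the illustrations mostly shrink the effect, which is conservative.

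The Adjusted Composite analysis also yields an MI result and a model-based by-visit result for most overlapping endpoints. For continuous endpoints, however, both of those assume MAR. Finally, parts of the sections defining the other endpoints are blacked out, so a rationale may exist that cannot be seen. All of this limits the weight of the point. None of it explains why MCAR was preferred to models the SAP already specifies.

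**Conclusion.** The point holds as a small improvement. The supportive Treatment Policy analyses through Week 24 rest on an assumption that the SAP does not justify and that its own imputation notes make doubtful. For the overlapping endpoints they also produce a second estimate with no stated precedence. This is clearest for ACR 20 and HAQ-DI change at Week 24. It applies too to ACR 50, ACR 70, MDA, SF-36 PCS, FACIT-F and PASI 90, once the FAS versus FAS-UKR wording is settled where it conflicts.

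Any bias is potential, and every figure above depends on assumed missing rates and dependence. The consequence is limited because these analyses are supportive and outside the type I error family. The primary and major secondary conclusions do not depend on them.

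**What to change.** In SAP 5.3.6.2.9, Table 5 and the Treatment Policy blocks of Tables 8 to 10, for visits through Week 24:

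- For overlapping endpoints and visits, report the existing MI result and name it as the Treatment Policy estimate. Appendix 12 already specifies these imputations for this estimand in FAS-UKR.
- For the remaining endpoints and visits, use the Appendix 13 MMRM (continuous) or GLMM (binary) on all observed data under MAR, whether or not an intercurrent event occurred. These models remain valid if the data are in fact MCAR.
- Label any observed-case summary that is kept as descriptive.
- Reconcile 5.3.5.2.2 (FAS) with Table 7 and Appendix 12 (FAS-UKR), and correct the FAS-URK misprint in 5.3.5.4.2.

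The cost is SAP wording and minor extra programming. The GLMM with an unstructured covariance may fail to converge for some endpoints, but Appendix 13 already lists fallback structures (Toeplitz, then first-order autoregressive moving average). Nothing changes after Week 24, where no treatment comparisons are planned.
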